8.2. Analysis of endpoints

For all primary aims, data will be analyzed using a mixed model two-way analysis of variance examining the effects of treatment group, time and factor interactions, such as radioactive iodine dose. Evaluation time periods (pre-surgery, Day 12, Week 6, Month 6, and 1 Year) will serve as between subjects factor and treatment group (prophylactic CND versus no CND) will serve as the between subjects factor. Experiment-wise error will be controlled with an appropriate adjustment to the alpha-level. Prior to each analysis, we will plot all data and carefully examine each analysis to ascertain that the assumptions of ANOVA are not violated. Data will be transformed as necessary to better conform to the assumptions. Nonparametric statistics will be used when assumptions for ANOVA are not achieved. Statistical support for the study design and analysis will be performed by [name] who will perform analyses with SAS statistical software (SAS Institute Inc., Cary, NC).

9. Risks and benefits of trial participation

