2.1. Primary outcome and endpoints

To determine the rate of transient and permanent hypocalcemia:

- Transient hypoparathyroidism as defined by a Day 1 serum parathyroid hormone (PTH) level of <10 pg/ml
- Post-operative serum calcium (mg/dL) and PTH (pg/ml) at Day 12 and Month 6

- Total calcium consumption in first 2 weeks (total gm)
- Hypocalcemia symptoms in first 2 weeks (average episodes/day)
- Hypocalcemia symptom severity scale (range of 1-5)
- Requirement for calcium and calcitriol at Month 6 (or, if laboratory values at visit reveal calcium < 8 mg/dL and PTH <15 pg/ml)

Calcium and PTH levels, calcium intake, and hypocalcemia symptoms will be monitored post-operatively (at Day 1, Day 12, and Month 6) to examine how parathyroid function is affected by a CND.

Hypoparathyroidism can lead to paresthesias and muscle cramps and is a known complication of total thyroidectomy, requiring frequent treatment with calcium and vitamin D. This risk is increased with a CND and is thus important to quantify when examining the risk/benefit ratio. Because calcium supplementation is routinely administered for symptoms of hypocalcemia in the post-operative period and this may impact the interpretation of laboratory evaluations, we will be evaluating a variety of metrics to assess the incidence and impact of hypocalcemia on patients.

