It is difficult to coordinate voice and swallow evaluations with regularly scheduled patient visits. If the study team is unable to schedule these procedures on the same day, the subject is given the option of returning on a different day of his or her choosing or waiving the evaluation(s) in question at that time point. If an exam is missed, the exam will be scheduled at the subject's next time point. To adequately address the secondary endpoints of the study, the study staff only needs to know if the vocal cord is working and, if it is not working, if it recovers; this can be assessed with only one post-operative time point. Ideally, the study team also hopes to understand the time course of recovery after surgery; therefore, we aim to evaluate patients at each time point. The research-only voice and swallow evaluations do not affect clinical care for thyroid cancer patients.

Subjects will receive an unstimulated thyroglobulin test approximately 6 weeks after surgery. Thyroglobulin reaches its nadir 3-4 weeks post-operatively in most patients, making the Week 6 time point ideal for collection. In multivariate analysis, the postoperative thyroglobulin level is often found to be an independent predictor of persistent or recurrent disease with a level above 0.2 ng/mL considered "elevated". Based on this result as well as the pathology report, the subject's treating endocrinologist will determine his or her risk status. According to the 2015 American Thyroid Association Management Guidelines for Adult Patients with Thyroid Nodules and Differentiated Thyroid Cancer, RAI remnant ablation is not routinely recommended after thyroidectomy in low-risk patients, although consideration of specific features of the individual patient that could modulate recurrence risk, disease follow-up implications, and patient preference are relevant to decision making regarding RAI. We will not require low-risk patients to undergo RAI remnant ablation in accordance with these guidelines; instead, their low risk status and thyroglobulin level < 0.2 ng/mL will classify their response to therapy as excellent. Should low-risk patients choose to undergo RAI remnant ablation, they will follow the protocol outlined below.

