In all intermediate- and high-risk subjects and low-risk subjects who choose to undergo RAI remnant ablation therapy, radioactive iodine will be administered at 4-20 weeks post-operatively and will be administered with rTSH. For consistency all subjects will be treated with 50 mCi of radioactive iodine unless it is strongly recommended otherwise based on specific features of the individual patient. Microscopic nodal involvement found on pathologic review will not influence the treatment dose of radioactive iodine, but the presence or absence of micrometastatic versus macrometastatic disease will be tracked for future analyses. Thyroglobulin levels will be checked after the rTSH stimulation in order to assess the burden of disease prior to radioactive iodine treatment. Following radioactive iodine administration, levothyroxine will be administered to maintain TSH < 0.5 uIU/mL. Labs will be checked at 6-8 week intervals until TSH level is in the goal range and stable.

At Month 6 and 1 Year visits, TSH, unstimulated thyroglobulin and anti-thyroglobulin antibody will be measured. Additionally, all patients will receive a neck ultrasound at these time points to further evaluate for recurrence.

If the subject underwent RAI remnant ablation, recombinant TSH will be administered and a blood sample testing for the stimulated thyroglobulin level will be obtained at the 1 Year visit. If the stimulated thyroglobulin is greater than 2 ng/mL and the neck ultrasound is negative, a whole body scan will be obtained. Elevated thyroglobulin and/or positive whole body scanning will prompt further evaluation with ultrasound, CT, MRI, or CT-PET as needed. All participants will be followed for a minimum of 1 year after treatment. Long term follow-up tracking the incidence of disease recurrence will be conducted throughout the entirety of the study, with the goal of tracking patients beyond the active study phase through our prospective endocrine surgical database.

Long-term follow-up: Participants who receive a diagnosis of PTC, as confirmed by final surgical pathology, and continue to receive care within the University of Wisconsin Hospital system will be followed through chart review and the endocrine surgery outcomes database until their cancers recur or they are lost to follow up. Clinical documentation of cancer recurrence only, if it occurs, will be abstracted from their electronic medical records.

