5.4. Allocation to intervention

Patient allocation will be randomized by using a permuted block randomization stratified by age (\geq or $<$ age 45) as the staging of thyroid cancer is different based on patient age, and tumor size (T1-T2 vs. T3) as the benefit of prophylactic central neck dissection may be greater in patients with T3 tumors. We have no predefined recruitment goal for participants \geq or $<$ age 45. For tumor size we would like to recruit 25% of patients with T3 tumors (size $>$ 4 cm or minimal extrathyroidal extension); this is estimated to be 25% of our eligible population, so we believe that this goal is achievable. Randomization will occur on the day of surgery in the operating room after confirming no suspicious adenopathy and will only be known by the operating surgeon. Participants will be blinded to their treatment allocation until their 2-week follow up appointment at which time their pathology report will be reviewed and they will be told of their treatment allocation.

6. Participant recruitment and consent

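### Section 8.2 names radioactive iodine dose, a post-randomisation variable that the arm may affect, in the only model for the primary aims and specifies no primary comparison without it

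*Combined protocol and SAP*

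**What the plan says.** Section 8.2 gives one method for all primary aims: a mixed-model "two-way analysis of variance examining the effects of treatment group, time and factor interactions, such as radioactive iodine dose". It describes two factors, treatment group and time. The time points are pre-surgery, Day 12, Week 6, Month 6 and 1 Year. It does not say whether iodine dose enters as a main effect, as an interaction with arm or time, or only in a supporting analysis. No primary analysis without iodine is named.

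On timing, Section 5.4 states: "Randomization will occur on the day of surgery in the operating room after confirming no suspicious adenopathy". Section 3 (post-operative follow-up) states that "radioactive iodine will be administered at 4-20 weeks post-operatively and will be administered with rTSH".

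On who receives iodine, the same part of Section 3 describes a thyroglobulin test about six weeks after surgery and continues: "Based on this result as well as the pathology report", the endocrinologist sets the patient's risk status. Intermediate- and high-risk patients are given iodine. Low-risk patients need not have it but may choose it. The dose among treated patients is standardised at 50 mCi, with exceptions allowed, and microscopic nodal disease is not to alter that dose.

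The primary items in Section 2.1 include "Transient hypoparathyroidism as defined by a Day 1 serum parathyroid hormone (PTH) level of <10 pg/ml" and "Post-operative serum calcium (mg/dL) and PTH (pg/ml) at Day 12 and Month 6". The others are calcium intake, symptom frequency and symptom severity from the two-week log, and the need for calcium and calcitriol at Month 6.

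**The concern.** The two arms are comparable because of randomisation, and that holds only for comparisons that do not condition on later events the arm can influence. Iodine is such a later event. If the arms differ in who receives it, comparing CND with no CND at a fixed iodine status sets patients who reached iodine by one route against patients who reached it by another. The result then mixes the effect of surgery with differences in disease burden. If iodine itself affected a Month 6 outcome, adjusting for it would also remove part of the total effect of the assigned strategy.

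A patient-level dose factor in a repeated-measures model also applies to that patient's pre-surgery and Day 12 values, which come before the iodine and cannot be caused by it. At stake is the randomised estimate for the repeated calcium and PTH measurements and for the Month 6 items, which bear on permanent hypoparathyroidism.

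**Working it through.** **1. Timing.** Count calcium and PTH separately by visit.

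| Primary measurement (Section 2.1) | Number | Latest day | Relation to iodine |
|---|---|---|---|
| Day 1 PTH | 1 | 1 | before |
| Day 12 calcium, PTH | 2 | 12 + 8 = 20 (window in the schedule of activities) | before |
| Two-week intake, symptom frequency, severity | 3 | log returned at the Day 12 visit, so 20 | before |
| Month 6 calcium, PTH, supplement need | 3 | Month 6 | after |

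The earliest iodine is at 4 × 7 = 28 days. So 1 + 2 + 3 = 6 of 9 measurements are complete before any iodine, and 3 of 9 follow it.

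**2. Can the arm change iodine use?** The documents suggest three routes.
- Pathology: Section 1.1 puts microscopic central-node disease at 60% of cases. Arm 2 removes those nodes and Arm 1 leaves them, so the pathology reports can differ by arm.
- Thyroglobulin: Section 2.2 uses the pre-iodine level to judge how complete the excision was, so it is partly a result of the operation.
- Choice: participants learn their arm at Day 12, before the iodine decision, and low-risk patients may opt for iodine.

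The rule on microscopic nodes covers the dose. It does not say such nodes cannot affect risk class or whether iodine is given. With a 50 mCi default and no requirement for low-risk patients, the dose variable is mainly 0 versus 50, and the rule does not cover that contrast.

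**3. The plan's own figure.** Section 8.1 assumes 12% vs 36%, power 0.8 and alpha 0.05 (two-sided assumed here). With mean rate 0.24 and difference 0.24:

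n = [1.96 × √(2 × 0.24 × 0.76) + 0.8416 × √(0.12 × 0.88 + 0.36 × 0.64)]² / 0.24² = (1.184 + 0.488)² / 0.0576 ≈ 48.5

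Continuity correction: (48.5 / 4) × [1 + √(1 + 4 / (48.5 × 0.24))]² ≈ 56.5, so 57 per arm and 114 in total, against the stated 58 and 116. This is an unadjusted comparison of two proportions with no iodine term, so this point does not alter the sample size.

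**4. Size of the possible bias.** The documents give no iodine rate by arm, so these inputs are assumptions. The true CND effect is 0.50 SD. A latent disease burden raises iodine use and has the stated correlation with the outcome. Iodine itself has no effect on the outcome. In least squares:

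adjusted effect = unadjusted effect − γ × δ

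Here δ is the difference between arms in iodine use, and γ is the iodine coefficient with arm in the model. Simulation gives:

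| Iodine use, Arm 1 vs Arm 2 | Burden-outcome correlation | Adjusted effect (SD) |
|---|---|---|
| equal | 0 to 0.5 | 0.50 |
| any | 0 | 0.50 |
| 50% vs 60% | 0.5 | 0.50 − 0.41 × 0.10 ≈ 0.46 |
| 50% vs 70% | 0.5 | 0.50 − 0.42 × 0.20 ≈ 0.42 |
| 42% vs 61% | 0.3 to 0.5 | 0.45 to 0.41 |
| 42% vs 70% | 0.3 to 0.5 | 0.42 to 0.37 |

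The lowest value is (0.50 − 0.37) / 0.50 = 26% below the truth. The unadjusted model returns 0.50 in every row.

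**5. If iodine itself shifts a Month 6 outcome** by 0.2 to 0.4 SD, with 50% use in Arm 1 and 62% or 73% in Arm 2, the total effect runs from 0.50 + 0.2 × 0.12 ≈ 0.53 (simulated) to 0.50 + 0.4 × 0.23 ≈ 0.59. The adjusted model still returns about 0.50, so it misses that part of the total effect.

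**The case against.** A reader might infer from Section 8.2 that the CND effect is adjusted for a consequence of the arm. The documents do not support that as fact, for four reasons.

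- Arm dependence is not shown. No iodine rate by arm is given, the dose is standardised, microscopic nodes may not alter it, and a footnote to Section 7.1 regards low-dose ablation as suitable for all patients. This limits the route through dose among treated patients. The route through whether iodine is given at all stays open, but it is plausible rather than established.
- The wording is loose. Iodine dose appears as an example of interactions to be examined. An effect-modification analysis, separate from the main estimate, is an equally available reading. That is a fair point, but the plan names no iodine-free primary comparison, so the ambiguity needs resolving.
- A reader might also infer that the sized endpoint is compromised. Section 8.1 places the primary endpoint at post-operative Day 1, which is not among the model's time points. The two-week log items are collected once, so they do not clearly enter a group-by-time model either. The clear reach is the repeated calcium and PTH analyses, plus Month 6 supplement need under the statement that the model covers all primary aims.
- The bias may be nil. It needs both arm-dependent iodine use and a link between iodine, or what drives it, and the outcome. No document supports a correlation between disease burden and calcium or PTH, and excluding T4 tumours and, from the randomised arms, nodal disease narrows burden.

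A further complaint, that the interaction wastes degrees of freedom, carries little weight. With iodine coded yes or no it costs one, in 70-140 patients.

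**Conclusion.** The concern holds in a limited form. Section 8.2 names a post-randomisation variable that may be affected by the arm, in the only model for the primary aims, and leaves open whether the reported CND effect is conditioned on it. If it is, the repeated calcium and PTH analyses and the Month 6 items are not a clean randomised comparison. Iodine cannot explain any primary item collected by Day 12 or in the first two weeks.

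Under the assumed inputs the adjusted effect lies between 0.50 SD (no bias) and about 0.37 SD for a true 0.50. These figures show the mechanism and a rough scale and are not a forecast. The sign in the real trial is unknown: finding nodes at pathology could raise iodine use after CND, a lower thyroglobulin could reduce it, and the link to the outcome could run either way. The Day 1 endpoint and the sample size of 116 stand. Severity: should fix. It is a free improvement, because a comparison without iodine keeps the protection of randomisation whichever assumption is true.

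**What to change.** In Section 8.2, delete the mention of radioactive iodine dose from the primary model. State that the primary arm comparison excludes iodine and adjusts only for variables fixed before randomisation, such as the age and tumour-size strata in Section 5.4. Report iodine receipt and dose by arm descriptively, as post-randomisation outcomes. Label any iodine-adjusted or iodine-interaction analysis of Month 6 or 1 Year outcomes as exploratory.

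The cost is a short edit to one section, made before the analysis. It needs no new data, no extra patients and no change to clinical care.

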8.1. Sample size determination

At the beginning of this study, we anticipated randomizing 140 patients with clinically node negative thyroid cancer, with the goal of 116 participants completing the study. Patients will be recruited from the Endocrine Surgery and Otolaryngology Clinics at the University of Wisconsin Hospitals and Clinics. This is a high volume tertiary care center with a large thyroid practice, performing approximately 350 thyroid operations per year. Thyroid cancer accounts for 30% of thyroidectomy cases at our institution and this is the pool from which the patients will be identified (approximately 105 patients/year). Approximately 15% of thyroid cancer cases will have a positive pre-operative ultrasound, thus decreasing our pool of eligible participants to approximately 89 patients per year. With an accrual goal of 140 participants within 4 years, we would need to recruit 39% of eligible patients each year.

Permanent complications in thyroid surgery are uncommon, but these complications can be disastrous for a patient that is affected. Permanent hypoparathyroidism occurs in 1-2% of patients after a total thyroidectomy and the risk may be as high as 14% when a CND is performed. The best surrogate marker to predict an increase in permanent morbidity is the incidence of transient hypoparathyroidism, which is substantially more common than permanent hypoparathyroidism. For example, transient hypoparathyroidism occurred in 12% of our last 270 patients undergoing a total thyroidectomy. The rate of transient hypoparathyroidism in patients treated with a CND has been shown in the literature to be significantly higher. The rate of transient hypoparathyroidism in recent large retrospective studies was reported to be between 38-51%.

We assumed a power of 0.8 and an alpha of 0.05. For sample size calculations we made the assumption that the incidence of transient hypoparathyroidism after a total thyroidectomy alone is 12% and that an increase to 36% (or tripling of the risk) is clinically significant. The rate of hypoparathyroidism in Arm 1 is based upon our last 270 patients and is a reliable estimate. The incidence in the CND arm is based on a

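### Section 8.2 sends all primary aims to an ANOVA whose time levels leave out Day 1, so the yes/no Day 1 PTH endpoint behind the original 116 has no named between-arm test

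*Combined protocol and SAP*

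**What the plan says.** **Endpoint.** Section 2.1 opens its list under the primary outcome with "Transient hypoparathyroidism as defined by a Day 1 serum parathyroid hormone (PTH) level of <10 pg/ml". The parathyroid measures are to be "monitored post-operatively (at Day 1, Day 12, and Month 6"). The same section puts permanent hypocalcemia inside the primary outcome, through the Month 6 items.

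**Sizing.** Section 8.1 states: "We assumed a power of 0.8 and an alpha of 0.05". It takes 12% with total thyroidectomy alone and 36% with CND, arrives at 58 per arm, and identifies post-operative Day 1 as the time of the primary endpoint. Sidedness is not given.

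**Analysis.** Section 8.2 states: "For all primary aims, data will be analyzed using a mixed model two-way analysis of variance". The time levels are "Evaluation time periods (pre-surgery, Day 12, Week 6, Month 6, and 1 Year"), and these levels "will serve as between subjects factor and treatment group" is described in the same way. The section adds: "Nonparametric statistics will be used when assumptions for ANOVA are not achieved". On multiplicity it says: "Experiment-wise error will be controlled with an appropriate adjustment to the alpha-level".

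**Randomisation.** Sections 3 and 5.4 stratify by age (45 or over versus under 45) and tumor size (T1-T2 versus T3). Section 8.2 mentions neither factor.

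**The concern.** The outcome that justified the original sample size is a proportion at one time point. The only analysis in the plan is a model for repeated measurements at other time points. Read literally, Section 8.2 never makes the 12% versus 36% comparison.

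The endpoint, threshold, day and arms are fixed. The test, its sidedness, the use of the strata and the alpha left after the promised adjustment are not. They would have to be chosen after the examination of preliminary data that Section 8.1 reports, and that weakens any claim that the main comparison was prespecified.

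**Working it through.** **1. Reproduce the 116.** Inputs from Section 8.1: p1 = 0.12, p2 = 0.36, alpha 0.05, power 0.80. Assumed: two-sided. Then mean p = 0.24, d = 0.24, z = 1.960 and 0.8416.

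- Uncorrected: n = [1.960·√(2·0.24·0.76) + 0.8416·√(0.12·0.88 + 0.36·0.64)]² / 0.24² = (1.184 + 0.488)² / 0.0576 = 2.794 / 0.0576 = 48.5, so 49 per arm.
- Continuity-corrected: n′ = (n/4)·[1 + √(1 + 4/(n·d))]² = (48.51/4)·[1 + √1.3435]² = 56.5, so 57 per arm (114 in all).
- If 49 is carried forward instead of 48.51, n′ = 57.03, which rounds up to 58, the stated figure.
- One-sided versions give 39 (uncorrected) or 47 (corrected) and do not match.

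The trial was therefore sized for a two-group comparison of proportions, and the figure is not in error.

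**2. Look for that comparison in Section 8.2.**

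| Visit | Primary outcome monitored (2.1) | Calcium and PTH scheduled (7.1) | Time level in 8.2 |
|---|---|---|---|
| Pre-surgery | no | yes | yes |
| Day 1 | yes | yes | **no** |
| Day 12 | yes | yes | yes |
| Week 6 | no | no | **yes** |
| Month 6 | yes | yes | yes |
| 1 Year | no | only if Month 6 is abnormal | yes |

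The grid holds two of the three visits in Section 2.1. The missing one is the visit of the powered endpoint. No chi-square, Fisher, logistic or other binary method appears anywhere in the document.

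**3. Does the choice of test matter?** Exact power for 12% versus 36% at two-sided 0.05:

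| Per arm | Fisher | Pearson |
|---|---|---|
| 35 | 0.57 | 0.66 |
| 58 | 0.83 | 0.88 |
| 70 | 0.90 | 0.93 |

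**4. Cost of using the strata.** Simulation with 40,000 trials per case and four strata; 25% T3 from Section 5.4; ages split evenly and blocks of 4 assumed.

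- The stratified Mantel-Haenszel test has type I error 0.047-0.051 in every case tried.
- With equal event rates across strata, power at 58 per arm is 0.875 stratified and 0.878 unstratified.
- If the T3 rate is three times the T1-T2 rate (assumed), power is 0.912 and 0.892.

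**5. The between-subjects wording, taken literally.** With three visits (pre-surgery, Day 12, Month 6) and within-patient correlation r, the group mean square is inflated by 1 + 2r while the error term is not. Type I error is then about P(|Z| > 1.96/√(1 + 2r)). For r = 0.3, 0.5 and 0.7 (assumed; the documents give no value) this is 0.12, 0.17 and 0.21. Simulated ANOVAs at 58 per arm give 0.118, 0.167 and 0.208.

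**The case against.** The best defence is that any statistician would compare the Day 1 proportions without being told to. The Summary promises to compare the cohorts on transient hypocalcemia, and Section 2.1 fixes the day and threshold. A yes/no outcome fails ANOVA assumptions, which triggers the nonparametric clause.

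Much of this stands. The remaining freedom is narrow, and it would be wrong to infer that the Day 1 rates will go unreported. What is absent is the formal test. The fallback names none, and it changes the method rather than the visits analysed.

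Other stronger readings are tempting, but the documents do not support them:

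- **The error rates of the calcium and PTH models are wrong.** Section 8.2 calls the model mixed, so labelling time a between-subjects factor is probably a slip for within-subjects. The 0.12-0.21 applies only if the label is followed literally.
- **The other items in Section 2.1 are really secondary.** The Blinding paragraph of Section 3 calls only subjective symptoms and calcium intake secondary. It says nothing about Month 6 permanent hypoparathyroidism, which Section 2.1 keeps in the primary outcome.
- **The 12% versus 36% contrast supports the whole current range of 70 to 140.** It supports the original 116. Section 8.1 bases the minimum of 70 on the adequacy of the qualitative data.
- **Preliminary data were compared by arm.** Section 8.1 does not say so.

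**Conclusion.** The point holds and should be fixed before analysis. As written, Section 8.2 has no between-arm test of the Day 1 yes/no endpoint that Section 8.1 treats as primary and on which the original 116 rests. This follows from the text alone.

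A reader might infer that the sample size is wrong or that the alpha adjustment erodes its power. Neither is shown. The 116 is reproduced to within two patients, on the assumption of a two-sided test, and the adjustment is not specified, so its effect on the Day 1 test may be zero.

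The Week 6 time level and the label on the time factor are minor. The strata are also a small matter: ignoring them costs nothing if event rates are equal across strata, and about 0.02 in power at 58 per arm if T3 rates are threefold.

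**What to change.** In Section 8.2:

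- **Primary analysis.** Compare the proportion with Day 1 PTH below 10 pg/ml between Arms 1 and 2, as randomised, at 0.05, and state the sidedness (two-sided fits the 116). Use a Mantel-Haenszel test stratified by age (under 45 versus 45 or over) and T stage (T1-T2 versus T3), and report the Mantel-Haenszel risk difference with a 95% CI. Base the lead role of Day 1 on Section 8.1.
- **Other items in Section 2.1.** Leave Month 6 permanent hypoparathyroidism within the primary outcome. Reconcile Section 2.1 with the Blinding paragraph of Section 3 on symptoms and calcium intake only. Name the promised experiment-wise adjustment. Options include a fixed sequence after Day 1, or Holm among the remaining items once the Day 1 test succeeds. Without such gating, two independent families each at 0.05 would give 1 − 0.95² = 0.0975.
- **Mixed model.** Keep it for continuous calcium and PTH at the visits where they are collected, with time as a within-subject factor.

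The cost is wording; no new visit or patient is needed. Under gating, the other items lose their confirmatory test if Day 1 fails. The change must be documented as made after preliminary data were examined. The Schedule of activities marks Day 1 PTH as standard of care, done as needed, so the text should also say how a missing value is handled.
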